7.6. Runtime

Since 12 August 2016.

7.7. Primary analysis

The association between changes in clinical examination findings over 24 hours and changes in cardiac output.

7.8. Secondary analysis

The association between changes in clinical examination, biochemical, and haemodynamic variables over 24 hours and 90-day mortality.

8. Right ventricular function and acute kidney injury

8.1. Research questions

Is RV-volume overload measured by tricuspid insufficiency and RV-diameters associated with acute kidney injury (AKI)?

Are clinical examination, biochemical, and haemodynamic variables associated with the development of AKI in patients without known pre-existent chronic kidney disease?

8.2. Variable of interest

Right ventricle diameters and tricuspid regurgitation velocity have been measured with the cardiac probe M3S of M4S with default cardiac imaging setting of the General Electric Vivid-S6 mobile ultrasound machine. The measurements were obtained in the AP4CH view with a right ventricle centred view. AKI was established and classified following the kidney disease: improving global outcomes (KDIGO) criteria. Urine output and serum creatinine measurements from the first 72 hours of inclusion were analysed to establish and classify AKI for each patient.

8.3. Timing of measurement

During inclusion in basic study (one-time snapshot).

8.4. Additional exclusion criteria

None.

8.5. Sample size, power and detectable difference

In our design paper, we have 489 patients who developed AKI and 418 patients with a normal renal function (controls). Pilot data from our design paper indicate that the AKI proportion among controls is 0.54. We will be able to detect true relative risks of 0.80 or 1.20 in exposed patients relative to unexposed patients with probability (power) 0.80. The type I error probability associated with this test of the null hypothesis that this relative risk equals 1 is 0.015.

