Sedative type, dose, speed	B	X	X			
Auscultation: souffles	B, 2, 7, 10	X	X			
Auscultation: crepitations	B, 2, 7, 10	X	X			
Auscultation: rhonchi	B, 2, 10	X	X			
Capillary refill: sternum	B, 7	X	X			
Capillary refill: index finger	B, 7	X	X			
Capillary refill: knee	B, 1, 7	X	X			
Temperature: subjective	B, 7	X	X			
Temperature: central	B, 7	X	X			

Temperature: peripheral at big toe and dorsum of foot	B, 7	X	X			
ΔTemp: central-to-peripheral	B, 7	X	X			
Mottling score at the knee	B, 1, 6, 7	X	X			
Peripheral circulation estimation	B, 7	X	X			
Pump function estimation	B, 7	X	X			
Degree of training	B, 7	X	X			
Haemodynamic variables measured with CCUS						
LVOT diameter	B, 6	X				X (validation in Corelab)
Peak flow velocity	B, 6, 7	X	X			X (validation in Corelab)
Velocity time integral	B, 6, 7	X	X			X (validation in Corelab)
Heart rate (echo)	B, 6, 7	X	X			X (validation in Corelab)
Cardiac output	B, 2, 3, 6, 7, 9, 10	X	X			X (validation in Corelab)
Cardiac output, every hour	6	X (during 6 hours)				
B-lines on 6 locations	2, 4, 7, 10	X	X			
TAPSE	2, 7, 8	X	X			
RV S'	2, 7, 8	X	X			
Common carotid artery diameter, flow	5	X				
Subclavian artery diameter, flow	5	X				
Common femoral artery, diameter, flow	5	X				
Abdominal flow	5	X				
RV basal diameter	8	X				
RV mid cavity diameter	8	X				
RV longitudinal diameter	8	X				
Tricuspid regurgitation peak velocity	8	X				
Left myocardial strain (rate)	11	X				

Septal myocardial strain (rate)	11	X				
Right myocardial strain (rate)	11	X				
Other haemodynamic measurement devices						
NIRS: StO ₂ thenar & knee	1	X				
FloTrac: inclusion date and time	6, 7	X (during 6 hours)	X			
FloTrac: cardiac output every hour	6, 7	X (during 6 hours)	X (once)			
FloTrac: noradrenaline dose	6, 7	X (during 6 hours)	X (once)			
FloTrac: inotropic type, dose, and speed	6, 7	X (during 6 hours)	X (once)			
FloTrac: mottling score	6, 7	X (during 6 hours)	X (once)			
Additional clinical variables						
ICU admission date	B			X		
ICU admission time	B			X		
EMV score	B			X		
Admission reason	B			X		
Patient admission specifics	B			X		
Shock type	B			X		
Final diagnosis	B			X		
X-Ray measurements	B			X		X
ECG measurements	B			X		X
Respiratory distress	10			X		
Direct ARDS risk factors	10			X		
Indirect ARDS risk factors	10			X		
SOFA score						X
SAPS II score						X
APACHE II score						X

APACHE IV score						X
Total ICU stay						X
Medical history						X
Biochemical variables						
Arterial blood gas variables	B			X		

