4.5. Sample size, power and detectable difference

In our design paper, we have 112 patients with an impaired TAPSE and 279 patients with a normal TAPSE (controls). Pilot data indicate that the 90-day mortality proportion among controls is 0.28⁷. We will be able to detect true relative risks of 0.46 or 1.62 in patients with impaired TAPSE relative to controls with probability (power) 80%. The type I error probability associated with this test of the null hypothesis that this relative risk equals 1 is 0.015. We will use an uncorrected chi-squared statistic to evaluate this null hypothesis.

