4.6. Runtime

Since 10 February 2016.

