8.6. Runtime

Since 25 October 2016.

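### The single detectable relative risk in sub-study 8, computed from 907 patients, cannot hold for the right-ventricular question, whose exposure was measured only from 25 October 2016

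*SAP*

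**What the plan says.** All places are in the SAP; section numbers beginning with 8 or 4.5 to 4.6 are in Appendix 1.

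- Section 8.5 counts patients by renal outcome: "In our design paper, we have 489 patients who developed AKI and 418 patients with a normal renal function (controls". It continues: "Pilot data from our design paper indicate that the AKI proportion among controls is 0.54". The result is: "We will be able to detect true relative risks of 0.80 or 1.20 in exposed patients relative to unexposed patients with probability (power) 0.80". The error rate is stated as: "The type I error probability associated with this test of the null hypothesis that this relative risk equals 1 is 0.015". No exposure is named.
- Section 8.7 lists two primary analyses. The first relates RV-volume overload (tricuspid insufficiency and RV diameters) to AKI. The second relates clinical, biochemical and haemodynamic variables to AKI.
- Section 8.3 makes the measurement a single one at inclusion, section 8.2 says it needs the AP4CH view, and section 8.6 gives the runtime as "Since 25 October 2016".
- Table 2 lists the RV diameters (for example "RV mid cavity diameter") and tricuspid regurgitation velocity at baseline under sub-study 8, with no mark in the retrospective column.
- For comparison, section 4.5 counts TAPSE values in the same design paper: "we have 112 patients with an impaired TAPSE and 279 patients with a normal TAPSE (controls". That sub-study started earlier: "Since 10 February 2016" (section 4.6).

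**The concern.** A detectable effect for an exposure-outcome association can count only patients in whom both were recorded. AKI can be classified across the cohort from urine output and creatinine. The RV exposure began part-way through recruitment. Main section 6.1.2 shows that the basic study took only the PLAX and AP5CH views, so patients included before the RV sub-studies would not have had the AP4CH view from which RV diameters could be read later.

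At stake is how the RV result can be interpreted. With 80% power for relative risks of 0.80 or 1.20, a null finding would carry some weight against effects of about 20%. With power near one third or lower, it would carry little.

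**Working it through.** **Step 1. Reproduce the plan's figure.** Inputs from section 8.5: p0 = 0.54, groups of 418 and 489, alpha 0.015. Sidedness is not stated; two-sided reproduces (z = 2.432), while one-sided would give power 0.86 to 0.87. For an uncorrected two-proportion test,

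power = Φ[(|p1 − p0| − z·SE0) / SE1],

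where SE0 = √[p̄(1 − p̄)(1/n0 + 1/n1)] and SE1 = √[p0(1 − p0)/n0 + p1(1 − p1)/n1].

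For a relative risk of 1.20, with 418 unexposed and 489 exposed:
- p1 = 0.54 × 1.20 = 0.648; difference 0.108
- p̄ = (418 × 0.54 + 489 × 0.648)/907 = 0.598
- SE0 = 0.03266; SE1 = 0.03257
- (0.108 − 2.432 × 0.03266)/0.03257 = 0.877, so power = 0.81

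For 0.80 the power is 0.79. Solving for power 0.80 gives 0.798 or 1.198, so the stated figure is reproduced with all 907 patients contributing an exposure value.

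**Step 2. Could 907 patients have the RV exposure?**
- Last inclusion: 1 November 2017 less 90 days (main section 3.4) = about 3 August 2017.
- RV window: 25 October 2016 to 3 August 2017 = 282 days.
- Earliest recruitment date shown: 1 April 2015 (Appendix 1, section 1.6), giving 855 days. The start of the basic study itself is not stated.
- Cohort size: 1075 (main section 3.2.1), so 1075/855 = 1.26 patients per day on average.
- Including 907 patients in the window would need 907/282 = 3.2 per day.

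The TAPSE count gives a check that needs no accrual assumption: 112 + 279 = 391 design-paper patients, and 391/907 = 43%, for a measurement that started about eight months earlier.

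**Step 3. Plausible number (assumption: even accrual).** 282/855 = 0.330. Then 0.330 × 1075 = about 355 of the whole cohort, or 0.330 × 907 = about 300 of the 907. Assumed starts between 1 March and 1 June 2015 move 355 to between 342 and 382.

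**Step 4. Recompute with p0 = 0.54 and alpha 0.015.** The exposed share is not given in the SAP, so it is varied.

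Worked case, N = 355 in equal groups, relative risk 1.20: p̄ = 0.594, SE0 = 0.05213, SE1 = 0.05181; (0.108 − 2.432 × 0.05213)/0.05181 = −0.363; power 0.36.

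Worked case, N = 355 with 71 exposed and 284 unexposed: p̄ = 0.562, SE0 = 0.0658, SE1 = 0.0639; result −0.816; power 0.21.

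| N with RV value | Exposed share | Detectable RR at power 0.80 | Power at RR 0.80 | Power at RR 1.20 |
|---|---|---|---|---|
| 907 (plan) | 0.539 | 0.80 or 1.20 | 0.79 | 0.81 |
| 391 | 0.50 | 0.70 or 1.30 | 0.38 | 0.40 |
| 355 | 0.50 | 0.68 or 1.31 | 0.34 | 0.36 |
| 355 | 0.30 | 0.65 or 1.34 | 0.28 | 0.29 |
| 355 | 0.20 | 0.60 or 1.39 | 0.21 | 0.21 |
| 300 | 0.50 | 0.65 or 1.34 | 0.29 | 0.30 |

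The 391 row borrows the TAPSE count as a favourable comparison. It is not a count of RV diameters.

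**The case against.** The strongest reply is that section 8.5 never says its figure serves the RV question. The second primary analysis uses variables collected in the basic study, so 907 may be broadly usable there, less patients with known chronic kidney disease (section 8.1). This stands. The criticism is therefore that one figure is given for two analyses and can fit at most one of them.

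Other points on that side also stand:
- The SAP gives no RV count, so 300 to 355 rests on even accrual and an assumed start date.
- Table 2 is weak evidence alone: it places TAPSE under sub-studies 2, 7 and 8 rather than 4, where it is the exposure. The argument rests on sections 8.2, 8.3 and 8.6 and main section 6.1.2.
- Main sections 2.2.3 and 7 defer sub-study analysis plans to later documents, the appendix calls sub-study conclusions explorative, and the 98.5% confidence intervals (main section 4.2) would show imprecision. This lowers the stakes but does not make the printed figure correct for the RV analysis.

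A reader might infer more than the document supports:
- That the arithmetic is wrong. It is not; it reproduces. The fault is in which patients are counted.
- That the 907 are the entire design-paper cohort. The SAP says only that these patients were in the design paper.
- That 0.68 or 1.31 is the right replacement. It needs near-equal exposure groups, and nothing in the SAP supports that; 489 and 418 are outcome groups.
- That the investigators will present a null result as excluding 20% effects. No passage says so.

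**Conclusion.** The point holds for the first primary analysis of sub-study 8 only. The stated power of 0.80 for relative risks of 0.80 or 1.20 needs all 907 patients to have an RV measurement. The runtime, the single measurement at inclusion and the imaging views rule that out.

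The size is less certain than the direction. Under even accrual, power for the stated effects is at most about 0.36, and about 0.21 at N = 355 with one patient in five exposed. Borrowing the 391 patients with TAPSE raises it only to 0.38 to 0.40. Unobtainable views would lower all of these. The exact detectable effect cannot be given from the SAP, because it contains neither the RV count nor the exposure split. The sub-study is exploratory and the basic study is unaffected, but the figure should be corrected because it is easily restated.

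**What to change.** In section 8.5, state that the 907-based figure applies to the second research question only. For RV-volume overload, add a separate detectable relative risk computed from the actual number of patients with a measured RV diameter or tricuspid regurgitation velocity, and from their actual exposed and unexposed numbers. If the split is not yet known, give a range of splits. Do not reuse the AKI and no-AKI counts as exposure groups, and do not insert 0.68 or 1.31 as the new figure.

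In section 8.7, define the population of the first analysis as the patients with those measurements.

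The cost is a few sentences and one recalculation. No data collection or basic-study analysis changes. The downside is that the stated detectable effect becomes less favourable.

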8.6. Runtime

Since 25 October 2016.

8.7. Primary analyses

The association between RV-volume overload measured by tricuspid insufficiency and RV-diameters and AKI.

The association between clinical, biochemical, and haemodynamic variables and the development of AKI.

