8.8. Secondary analyses

The association between RV-volume overload measured by tricuspid insufficiency and RV diameters and 90-day mortality.

The association between clinical, biochemical, and haemodynamic variables and the development of AKI regardless of the presence of pre-existent chronic kidney disease.

9. Fluid responsiveness

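### Sub-study 8: the second primary analysis in 8.7 drops the chronic kidney disease restriction of its own research question, so as written it duplicates a secondary analysis in 8.8

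*SAP*

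**What the plan says.** All references are to the SAP, Appendix 1, sub-study 8, unless stated.

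- **8.1** asks two questions. The first, on right ventricular volume overload and acute kidney injury (AKI), names no restriction. The second asks whether clinical, biochemical and haemodynamic variables are "associated with the development of AKI in patients without known pre-existent chronic kidney disease". Table 1, row 8, carries the same two questions with the same restriction on the second only.
- **8.4** lists no additional exclusions.
- **8.5** counts 489 patients who developed AKI and "418 patients with a normal renal function (controls"). It does not say whether patients with chronic kidney disease are among these 907.
- **8.7** gives two primary analyses. The first is "The association between RV-volume overload measured by tricuspid insufficiency and RV-diameters and AKI". The second is "The association between clinical, biochemical, and haemodynamic variables and the development of AKI". Neither mentions chronic kidney disease.
- **8.8** gives as its second secondary analysis the same variables and the same outcome, "regardless of the presence of pre-existent chronic kidney disease".

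**The concern.** Section 8.7 is where the primary analyses of the sub-study are fixed. An analyst who follows it together with 8.4 includes everyone, and then meets the same instruction again in 8.8 under the label secondary. Two things follow. The question in 8.1 is left unanswered, because no listed analysis is restricted to patients without known chronic kidney disease. And the primary population is open: restricted according to 8.1 and Table 1, unrestricted according to 8.7. That leaves room to choose after both results have been seen, which the SAP's Discussion says the plan was drafted to avoid. The label matters too, since section 4.2 ties the 0.015 threshold to primary outcomes.

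**Working it through.** **1. The passages side by side, for the second question**

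| Place | Role | Population |
|---|---|---|
| 8.1 and Table 1 | research question | no known pre-existent chronic kidney disease |
| 8.4 | entry to the sub-study | no extra exclusion |
| 8.7, second line | primary analysis | none stated, so all patients |
| 8.8, second line | secondary analysis | all patients, explicitly |

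The predictors (clinical, biochemical, haemodynamic) and the outcome (development of AKI) are the same in 8.7 and 8.8. With no restriction in 8.7, nothing distinguishes the two lines.

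**2. The plan's own power figure**

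Inputs from 8.5: groups of 418 and 489, risk 0.54, relative risk (RR) 0.80 or 1.20, type I error 0.015, stated power 0.80. The test is taken as two-sided (8.5 does not say), so z = 2.432. The statistic is taken as the uncorrected chi-squared with pooled variance under the null.

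Power = Φ[(|p1 − p0| − z × SE_pooled) / SE_unpooled]. Here p0 = 0.54, p1 = 0.54 × RR and |p1 − p0| = 0.108 in both cases. Also 1/418 + 1/489 = 0.004437.

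- RR 1.20: p1 = 0.648. Pooled risk = (418 × 0.54 + 489 × 0.648)/907 = 0.598. SE_pooled = √(0.598 × 0.402 × 0.004437) = 0.03266. SE_unpooled = √(0.54 × 0.46/418 + 0.648 × 0.352/489) = 0.03257. Power = Φ[(0.108 − 0.0794)/0.03257] = Φ(0.877) = 0.810.
- RR 0.80: p1 = 0.432. Pooled risk = 0.482. SE_pooled = 0.03328. SE_unpooled = 0.03311. Power = Φ[(0.108 − 0.0810)/0.03311] = Φ(0.817) = 0.793.

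Solved for power 0.80, the detectable RRs are 0.798 and 1.198. Section 8.5 therefore reproduces.

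**3. The effect of restoring the restriction on 8.5**

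The SAP gives no prevalence of chronic kidney disease. The shares below are assumed. Patients are removed evenly from both groups and the risk is held at 0.54.

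| Share removed (assumed) | Patients left | Detectable RRs at power 0.80 |
|---|---|---|
| 0% | 907 | 0.798 / 1.198 |
| 5% | 907 × 0.95 ≈ 862 | 0.793 / 1.203 |
| 10% | 907 × 0.90 ≈ 816 | 0.788 / 1.208 |
| 20% | 907 × 0.80 ≈ 726 | 0.775 / 1.221 |
| 30% | 907 × 0.70 ≈ 635 | 0.760 / 1.235 |

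This keeps the set-up of 8.5, which uses the AKI and no-AKI counts as if they were exposure groups and takes 489/907 = 0.539 as the risk among controls. Whether that set-up is sound is a separate question.

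**The case against.** The strongest reply is that the intent is plain. Question 2 in 8.1 and Table 1 is restricted, and the wording of 8.8 makes sense as a contrast only if the primary analysis excludes chronic kidney disease. On that reading 8.7 has a slip of wording, not two analyses meant to be identical. This stands as an account of intent. It does not make 8.7 correct, because the line that defines the primary analysis still names the wrong population.

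Scope also lowers the stakes. Section 2.2.3 says the SAP guides the basic study, with sub-study SAPs to follow. The Discussion says those will be written before the sub-study hypotheses are analysed. Appendix 1 calls the sub-study conclusions explorative. This too stands. It makes the correction timely and cheap, since the mismatch would otherwise pass into the later document.

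A reader might infer three stronger points. The SAP does not support them.

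- *That 8.1 restricts the whole sub-study.* It restricts only the second question. The first primary analysis matches its own question.
- *That None in 8.4 is an error.* The secondary analysis in 8.8 needs patients with chronic kidney disease to be enrolled. An exclusion in 8.4 would make that analysis impossible.
- *That the first primary analysis is biased because chronic disease is counted as AKI.* AKI is classified by KDIGO (8.2), and including these patients does not by itself score chronic disease as AKI. Section 5.6 lists a history of chronic renal failure as a measured confounder of urine production, and the Discussion says primary outcomes will be adjusted for confounders. Any size put on such a bias would rest entirely on assumed inputs. The 907 would also be too many for right ventricular measurements that began only on 25 October 2016 (8.6). Restricting that analysis is a design preference.

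**Conclusion.** The point holds for the second primary analysis of sub-study 8. Section 8.7 omits the restriction that 8.1 and Table 1 place on the question, so as written it duplicates the second secondary analysis in 8.8 and does not answer the question. This follows from the text alone and needs no assumption.

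The numerical consequence is small. The power statement in 8.5 reproduces (0.793 and 0.810 against 0.80). If its 907 patients include chronic kidney disease and an assumed 5% to 10% are removed, the detectable RRs move from 0.80 and 1.20 to about 0.79 and 1.20 to 1.21. At an assumed 30% they would be about 0.76 and 1.24. These values depend on even removal from both groups and an unchanged risk of 0.54. Nothing here shows that the first primary analysis is wrong or that 8.4 needs changing.

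**What to change.** 1. In 8.7, extend the second primary analysis so that it concerns "the development of AKI in patients without known pre-existent chronic kidney disease", as 8.1 and Table 1 do.
2. Leave 8.4 at None and keep the unrestricted analysis as the secondary in 8.8.
3. In 8.5, state whether the 907 patients (489 and 418) include those with known chronic kidney disease. If they do, recount the groups and restate the detectable RRs for the restricted population.
4. Carry the corrected wording into the sub-study SAP that is to follow.

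The cost is one phrase and, if needed, a recount. No new data are required: Table 2 lists medical history and section 5.6 treats a history of chronic renal failure as measured. The downside is a slightly smaller number in the second primary analysis.

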8.8. Secondary analyses

The association between RV-volume overload measured by tricuspid insufficiency and RV diameters and 90-day mortality.

The association between clinical, biochemical, and haemodynamic variables and the development of AKI regardless of the presence of pre-existent chronic kidney disease.

9. Fluid responsiveness

9.1. Research question

What is the diagnostic accuracy of fluid responsiveness assessed by changes in end-tidal carbon dioxide (EtCO₂), heart rate and blood pressure compared to fluid responsiveness assessed by the passive leg raising (PLR) test?

What is the diagnostic accuracy of fluid responsiveness assessed by a PLR test without lowering the head of the bed compared to fluid responsiveness assessed by the standard PLR test?

9.2. Variable of interest

During the fluid responsiveness study, two different PLR tests were applied when supervised by the treating ICU physician. Every passive leg raising manoeuvre was conducted for a maximum duration of 60 seconds during which the changes in cardiac output, heart rate, blood pressures, central venous pressure, and EtCO₂ were recorded. Fluid responsiveness was diagnosed when cardiac output increased with 15% after the PLR-test. The PEEP-challenge was conducted in a similar manner as described in sub-study 3.

9.3. Timing of measurement

During inclusion in basic study (one-time snapshot).

9.4. Additional exclusion criteria

The attending ICU physician was not interested in fluid responsiveness at time of inclusion.

9.5. Sample size, power and detectable difference

Due to a set sample size we were able to estimate the precision of our estimate (i.e. the maximum marginal error). In our pilot data, the prevalence of fluid responsiveness was 45%, and EtCO₂ increase of 0.3 had a sensitivity of 83.3% and a specificity of 71.4%. Based on 20 included patients who underwent the PLR-test, a type-I error of 0.015 (with a corresponding Z-value of 2.17), and the abovementioned prevalence, sensitivity and specificity, the estimated maximal marginal error for sensitivity is 11.9% and 2.7% for specificity.

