4.2. Statistical significance and confidence interval

As calculated in 4.1, we will consider a $P < 0.015$ as statistically significant for our primary outcomes. When we find a $0.015 \leq P \leq 0.05$, we will consider this association of dubious significance and will emphasise the increased chance of a type I error. Results will be presented with their values (e.g. regression coefficients, odds ratios, etc.) with 98.5% confidence intervals.

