6.5.2. Diagnostic test evaluation

Depending on the optimal and number of cut-offs (i.e. low or normal cardiac index or low, normal and high cardiac index), we will display our diagnostic test in a 2 x 2 table, 2 x 3, or a 3 x 3 table (28,29). An example table can be found below. In a 3 x 3 table, data will be ordinal and we will give an indication of the agreement with the weighted kappa (30).

		Cardiac index cut-offs		
		Low (< 2.5)	Normal (2.5 to 4.5)	High (> 4.5)
EXAMPLE: Capillary refill time	Prolonged	True positive (a)	False positive (d)	False positive (d)
	Normal	False normal (b)	True normal (d)	False normal (b)
	Shortened	False negative (c)	False negative (c)	True negative (d)

Subsequently, we will calculate sensitivity, specificity, positive and negative predictive values and positive and negative likelihood ratios. Because this can only be calculated in 2 x 2 tables, we will cut the 3 x 3 table in low/normal and normal/high cut-offs:

		Cardiac index below/above x L/min/m ²	
		Yes	No
Clinical examination finding(s) present	Yes	True positive (a)	False positive (c)
	No	False negative (b)	True negative (d)

Explanation: x can be 2.2, 2.5, 4.0 or 4.5 L/min/m².

In addition, we will also calculate the 98.5% confidence intervals. Below we interpret each diagnostic test parameter for our diagnostic study.

- True positive: the number of patients with a low cardiac index who also had clinical examination signs indicating *hypoperfusion*.
- False positive: the number of patients without a low cardiac index, but with clinical examination signs indicating *hypoperfusion*.
- True negative: the number of patients without a low cardiac index and with clinical examination signs indicating *a normal* perfusion.
- False negative: the number of patients with a low cardiac index, but with clinical examination signs indicating *a normal* perfusion.
- Sensitivity: the probability of the presence of a low cardiac index when there were clinical examination signs indicating *hypoperfusion*.
- Specificity: the probability of the absence of a low cardiac index when clinical examination signs indicating *a normal* perfusion.
- Positive predictive value: the probability that a low cardiac index is present given the clinical examination signs indicate *hypoperfusion*.
- Negative predictive value: the probability that a low cardiac index is absent given the clinical examination signs indicate *a normal* perfusion.

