7.5. Sample size, power and detectable difference

We are planning to conduct this sub-study with 100 patients and we will regress their values of difference in cardiac output changes over 24 hours against clinical examination findings such as central-to-toe temperature difference. Prior data indicate that the standard deviation of central-to-toe temperature is 4.1 with an estimated standard deviation of the regression errors of 1.35. If the true slope of the line obtained by regressing changes in cardiac output against central-to-toe temperature differences is 0.16, we will be able to reject the null hypothesis that this slope equals zero with probability (power) 80%. The type I error probability associated with this test of this null hypothesis is 0.015.

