10.5. Sample size, power and detectable difference

Due to a set sample size we were able to estimate the precision of our estimate (i.e. the maximum marginal error). In our pilot data, the diagnosis of ARDS was 5.8%, and the presence of a B-profile had a sensitivity of 88.5% and a specificity of 64.5%. Based on pilot data of 446 included, a type-I error of 0.015 (with a corresponding Z-value of 2.17), and the abovementioned prevalence, sensitivity and specificity, the estimated maximal marginal error for sensitivity is 13.6% and 20.4% for specificity.

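### Appendix 9.5 states the precision of sub-study 2; the 10.5 specificity margin and the 7.5 power do not follow from their printed inputs; 8.5 and 11.5 treat outcome groups as exposure groups

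*SAP*

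**What the plan says.** Section 9.5 of Appendix 1 takes a fluid-responsiveness prevalence of 45% from pilot data, with an EtCO₂ criterion that "had a sensitivity of 83.3% and a specificity of 71.4" per cent. It applies these to the sub-study sample: "Based on 20 included patients who underwent the PLR-test, a type-I error of 0.015 (with a corresponding Z-value of 2.17". It concludes that "the estimated maximal marginal error for sensitivity is 11.9% and 2.7% for specificity". Section 2.5 ends with the same words, but for 446 radiographs, prevalence 18.6%, sensitivity 54.5% and specificity 93.8%.

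Section 10.5 (446 patients, ARDS prevalence 5.8%, sensitivity 88.5%, specificity 64.5%) says that "the estimated maximal marginal error for sensitivity is 13.6% and 20.4% for specificity".

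Section 7.5 plans 100 patients, a predictor SD of 4.1 "with an estimated standard deviation of the regression errors of 1.35", and claims 80% power for a slope of 0.16 at alpha 0.015.

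Section 8.5 says "we have 489 patients who developed AKI and 418 patients with a normal renal function (controls", gives an AKI proportion of 0.54 in those controls, and claims 80% power for relative risks of 0.80 or 1.20. Section 11.5 has 51 pilot patients with 9 deaths, a control mortality of 0.28, and 80% power for a relative risk of 3.0 between those who died and those who survived.

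In the main text, section 4.2 promises results "with 98.5% confidence intervals", and section 6.5.2 says of the accuracy measures that "we will also calculate the 98.5% confidence intervals".

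**The concern.** Two sub-studies with very different samples and test accuracies cannot share both margins to the decimal. A margin of 2.7 points on a specificity near 71%, from about 11 non-responders, is not attainable. Someone planning the sub-study from 9.5 would expect a tight estimate and obtain a very wide one.

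The other sections are questionable for different reasons. In 10.5 specificity appears less precise than sensitivity, although almost all patients are free of ARDS. In 7.5 the effect is large relative to the stated error SD. In 8.5 and 11.5 the outcome of the primary analysis (AKI in 8.7, 90-day mortality in 11.7) defines the groups being compared, so a relative risk of that outcome between the groups has no meaning. At stake are stated precision and power that the sub-studies may not have, and that could be carried into their own SAPs.

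**Working it through.** **Margins.** Formula: z·√(p(1−p)/n), with n = N × prevalence for sensitivity and N × (1 − prevalence) for specificity; z = 2.17 as printed.

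- 2.5: n = 446 × 0.186 = 83 and 446 × 0.814 = 363. Sensitivity 2.17·√(0.545·0.455/83) = 11.9%; specificity 2.17·√(0.938·0.062/363) = 2.7%. The stated pair is reproduced here.
- 9.5: n = 20 × 0.45 = 9 and 20 × 0.55 = 11. Sensitivity 2.17·√(0.833·0.167/9) = 27.0%; specificity 2.17·√(0.714·0.286/11) = 29.6%. The most favourable variant tried (z = 1.96, all 20 patients as denominator) still gives 16.3% and 19.8%.
- Patients needed for the margins stated in 9.5: 2.17²·0.833·0.167/(0.119²·0.45) = 103 for sensitivity; 2.17²·0.714·0.286/(0.027²·0.55) ≈ 2,400 for specificity.
- The normal limits in 9.5 pass 100%: 83.3 + 27.0 = 110.3 and 71.4 + 29.6 = 101.0. As an illustration only, Wilson 98.5% intervals at nearby whole counts are 38–95% (7/9), 48–99% (8/9), 30–88% (7/11) and 37–92% (8/11), each at least 50 points wide.
- 10.5: n = 446 × 0.058 = 25.9 and 446 × 0.942 = 420.1. Sensitivity 2.17·√(0.885·0.115/25.9) = 13.6%, as stated. Specificity 2.17·√(0.645·0.355/420.1) = 5.1%. Putting 25.9 in the specificity formula gives 20.4%, the printed figure.

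**The z-value.** 1 − Φ(2.17) = 0.0150, so 2.17 is the one-sided value. A two-sided 98.5% interval needs Φ⁻¹(0.9925) = 2.43; the ratio is 1.12. At 2.43 the margins (sensitivity / specificity) are 13.3% / 3.1% in 2.5, 30.2% / 33.1% in 9.5 and 15.3% / 5.7% in 10.5.

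**7.5.** Noncentrality = slope·SDx·√n/SDe = 0.16·4.1·10/1.35 = 4.86. The two-sided 0.015 critical t on 98 df is 2.48, so power is 0.99. Power of 80% corresponds to a slope of about 0.11, or, at slope 0.16, to a predictor SD of about 2.8. At the same two-sided alpha, standard methods give 0.80 to rounding for 1.5, 3.5, 4.5, 5.5 and 6.5, so 7.5 is the outlier.

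**8.5.** Uncorrected chi-squared, two-sided alpha 0.015. Entering 489 versus 418 as exposed and unexposed, with risk 0.54 in the unexposed, gives power 0.79 at RR 0.80 and 0.81 at RR 1.20, which is the printed claim. These groups are AKI and no AKI. Moreover 489/(489 + 418) = 489/907 = 0.539: the 0.54 is the whole-sample proportion, whereas among patients without AKI it is zero by definition. Keeping N = 907 and risk 0.54 but assuming other exposure splits:

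| Assumed exposed share | Power, RR 0.80 / 1.20 |
|---|---|
| 50% | 0.80 / 0.81 |
| 30% | 0.71 / 0.72 |
| 10% | about 0.31 for both |

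**11.5.** Entering 9 versus 42 with risks 3.0 × 0.28 = 0.84 and 0.28 gives power 0.82, close to the printed 80% (exactly 80% at RR 2.97). These groups are the dead and the survivors.

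**The case against.** The best defence is about consequence. Appendix 1 calls the sub-study conclusions explorative and requires external confirmation. Sections 2.2.3 and 7 leave the sub-studies to SAPs of their own. Section 9.5 describes its sample as already set, so the wrong margin determined no sample size. No decision rule uses any of these figures. All of this stands and limits the severity.

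On 7.5, one might infer that the error is harmless because power is only understated. The document does not support that. The SD of 4.1 is also given in 1.5, where temperature is measured once, while 7.5 analyses 24-hour changes. If the SD of the change were about 2.8, the 80% would be right and the input wrong.

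On 9.5, a reader might infer that 83.3% and 71.4% are impossible because 9 and 11 patients cannot yield them. But the section takes them from pilot data and never says that they came from the same 20 patients.

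On 11.5, a reader might see a contradiction between 0.28 and 9/51 = 0.18. The two come from different sources, and no time frame is given for the 9 deaths.

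The z-value point rests partly on inference: the 98.5% intervals are set in a plan scoped to the basic study. The 0.015 threshold in 4.1 is cohort-wide, so applying them to the sub-studies is reasonable, but the effect is only about 12%.

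**Conclusion.** The point holds as a set of appendix errors, of minor severity. The margins in 9.5 belong to 2.5; the half-widths that follow from its own inputs are about 2.3 times (27.0/11.9) and 11 times (29.6/2.7) those stated. The 10.5 specificity margin is four times too wide (20.4/5.1) because of a wrong denominator. In 7.5 the printed power and inputs are incompatible (0.99 against 0.80), and which of them is wrong is open. In 8.5 and 11.5 the stated 80% has no basis.

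No replacement power can be given for 8.5 or 11.5, because the exposure splits are not stated. At N = 907 and risk 0.54 the near-balanced 489/418 split gives about the highest power available, so an unequal exposure split would lower it; a gain would need a different unexposed risk. Sub-study 8 ran only from 25 October 2016, so the document does not show that all 907 had right-ventricular measurements. For that reason it would be unsafe to infer that 9.5 is the only section that promises too much.

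The margin results rest on the usual normal-approximation formula, confirmed by its reproduction of 2.5 and of the 10.5 sensitivity margin. Nothing here touches the basic-study analyses.

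**What to change.** - **9.5:** replace the copied margins with about 27% and 30% (30% and 33% at z = 2.43), and report Wilson or exact intervals, since the normal limits exceed 100%.
- **10.5:** restate the specificity margin as 5.1% (5.7% at z = 2.43).
- **z-value:** if 98.5% intervals are to be reported for the sub-studies, use 2.43 throughout: 13.3% / 3.1% in 2.5, 30.2% / 33.1% in 9.5 and 15.3% / 5.7% in 10.5.
- **7.5:** check whether 4.1 is the SD of the 24-hour change. If the inputs stand, state 99% power, or a detectable slope of 0.11 at 80%. Otherwise correct the SD.
- **8.5 and 11.5:** recalculate from exposure groups among the patients actually measured, with the outcome risk in the unexposed.

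The cost is appendix wording and a short recalculation, with no extra patients and no change to the basic study. Section 9.5 will look much less favourable. The 10.5 specificity margin will look better. The result for 7.5 depends on the SD check, and those for 8.5 and 11.5 on the exposure splits and unexposed risks.
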